Due to the need for multiple blood sampling, the volunteer has to stay at the study site for the first day after the injection.

Safety and tolerability assessment

Safety and tolerability will be assessed by monitoring vital signs (blood pressure, heart rate, and body temperature), conducting periodic physical examinations, assessing the frequency and severity of local reactions, and evaluating the results of complete blood count and blood biochemistry tests, urinalysis, and electrocardiography. These parameters will be assessed over a period of 71 days after a single-dose administration of the test drug. Additionally, information about the tenderness of subcutaneous injection, evaluated by a volunteer using a 10-point visual analog scale, will be analyzed.

Pharmacokinetic assessment

Pharmacokinetic assessment will be carried out based on data on the BCD-089 concentration in the serum of healthy volunteers. Volunteers included in the study arrive at the study site on the morning of the drug administration day. A venous catheter is installed immediately before the first blood sampling (the time from the catheter placement to the first blood sampling from it should not exceed one hour). Since multiple blood sampling is carried out only during the first day after the test drug administration, the time of placement a venous catheter will be 24 hours, after which the blood is taken by venipuncture. Detailed description of blood sampling points is presented in Table 3 below.

Translated from Russian to English, dated 06-Jul-2020

Pharmacodynamics and immunogenicity assessment

Pharmacodynamics assessment will be carried out based on data on the concentrations of C-reactive protein, soluble IL-6 receptor, human IL-6 in the serum of healthy volunteers.

Table 4. Detailed description of blood sampling for CRP, sIL-6R, IL-6 testing

Visit	Sample labeling number	Blood sampling time	Acceptable window for blood sampling	Blood volume (for 3 types of analyzed substances)
[REDACTED]	[REDACTED]	[REDACTED]	[REDACTED]	[REDACTED]
[REDACTED]	[REDACTED]	[REDACTED]	[REDACTED]	[REDACTED]
[REDACTED]	[REDACTED]	[REDACTED]	[REDACTED]	[REDACTED]
[REDACTED]	[REDACTED]	[REDACTED]	[REDACTED]	[REDACTED]
[REDACTED]	[REDACTED]	[REDACTED]	[REDACTED]	[REDACTED]
[REDACTED]	[REDACTED]	[REDACTED]	[REDACTED]	[REDACTED]
[REDACTED]	[REDACTED]	[REDACTED]	[REDACTED]	[REDACTED]
[REDACTED]	[REDACTED]	[REDACTED]	[REDACTED]	[REDACTED]
[REDACTED]	[REDACTED]	[REDACTED]	[REDACTED]	[REDACTED]

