5.3.1. Substitution of volunteers who withdrew from the study

The volunteers can be substituted in the following cases:

1. Volunteers who withdrew the study for reasons not related to administration of the study drug (missing visit, withdrawal of consent, systematic violation of visit windows, etc.).
2. Non-compliant volunteers (see Section 6.6).

Volunteers who withdrew from the study after administration of the study drug for safety reasons (AE that did not allow to come to a visit to perform the Protocol procedures) will not be replaced.

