6.6. Compliance assessment

In this clinical study, any volunteer is considered to be non-compliant if he:

- Missed more than one visit;
- Deviated from the scheduled window for more than one visit;
- Missed sampling of more than 2 blood samples for evaluation of pharmacokinetics and pharmacodynamics;
- Deviated from the scheduled window for pharmacokinetic and pharmacodynamic sampling by a time exceeding the acceptable deviation described in Tables 3 and 4.

Translated from Russian to English, dated 06-Jul-2020

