9. STATISTICAL METHODS

9.1 Calculation of the parameters of pharmacokinetics and pharmacodynamics

9.1.1. Pharmacokinetic parameters

Based on the calculated concentration values for the anti-IL-6 monoclonal antibody in the blood of each volunteer, the following pharmacokinetic variables will be estimated at time points specified in this protocol:

1. C_{\max} - maximum serum concentration of anti-IL-6 receptor antibody over the observation period.
2. t_{\max} - time to achieve maximum serum concentration (C_{\max}) of anti-IL-6 receptor antibody.
3. AUC_{0-1680} — the area under the concentration of anti-IL-6 receptor monoclonal antibody-time curve over the time interval from 0 to 1680 hours. AUC_{0-1680} will be calculated using the trapezoid method using the following formula, where C_p is the concentration of the drug BCD-089 in the blood at the time t_p in hours:

$$t_p \in \{0; 2; 8; 12; 24; 48; 72; 96; 120; 168; 240; 336; 504; 672; 1176; 1680\}_{p=1, \dots, 16}$$

4. $AUMC_{0-1680}$ - total area under the curve of the concentration of anti-IL-6 receptor monoclonal antibody multiplied by time over the time interval from 0 to 1680 hours. $AUMC_{0-1680}$ will be calculated using the following formula:

$$AUMC_{0-1680} = \sum_{p=2}^{16} \frac{(C_p * t_p + C_{p-1} * t_{p-1}) * (t_p - t_{p-1})}{2},$$

where C_p — concentration of anti – IL – 6

– receptor monoclonal antibody против рецептора ИЛ6

Translated from Russian to English, dated 06-Jul-2020

in the blood at t_p

$$t_p \in \{0; 2; 8; 12; 24; 48; 72; 96; 120; 168; 240; 336; 504; 672; 1176; 1680\}_{p=1, \dots, 16}$$

5. **Total clearance (Cl)** is a parameter that reflects the volume of test tissue, which is cleared from the anti-IL-6 receptor monoclonal antibody per unit of time and is determined by the ratio of the anti-IL-6 receptor monoclonal antibody dose (*DOSE*) to $AUC_{(0-1680)}$:

$$CL = \frac{DOSE}{AUC_{0-1680}}$$

6. **Mean residence time (MRT)** of the anti-IL-6 receptor monoclonal antibody molecule in the body will be calculated as the ratio of $AUMC_{0-1680}$ to AUC_{0-1680} :

$$MRT = \frac{AUMC_{0-1680}}{AUC_{0-1680}}$$

7. **Elimination constant** of the anti-IL-6 receptor monoclonal antibody (k_{el}) will be determined using the following formula:

$$k_{el} = \frac{1}{MRT}$$

8. **Half-life period** of the anti-IL-6 receptor monoclonal antibody ($T_{1/2}$) will be determined using the following formula:

$$T_{1/2} = \frac{\ln(2)}{k_{el}} = \ln(2) * MRT$$

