9.1.2. Pharmacodynamical parameters

Based on the obtained concentrations of C-reactive protein, IL-6 and soluble IL-6 receptor in the blood of each volunteer, the following pharmacodynamic parameters will be calculated at the Protocol-specified time intervals:

1. C_{\max} – maximum blood concentration of C-reactive protein, IL-6 and soluble IL-6 receptor over the observation period.
2. t_{\max} – time to maximum blood concentration (C_{\max}) of C-reactive protein, IL-6 and soluble IL-6 receptor.
3. AUC_{0-1680} – the area under the concentration-time curve for C-reactive protein, IL-6 and soluble IL-6 receptor over the time interval from 0 to 1680 hours. AUC_{0-1680} is calculated using the trapezoidal method with the following formula:

$$AUC_{0-1680} = \sum_{p=2}^{16} \frac{(C_p + C_{p-1}) * (t_p - t_{p-1})}{2},$$

where C_p concentration of C – reactive protein, IL – 6 and soluble IL
– 6 receptor values

ИЛ6 in the blood at t moment of time t_p (hours),

$$t_p \in \{0; 2; 8; 12; 24; 48; 72; 96; 120; 168; 240; 336; 504; 672; 1176; 1680\}_{p=1, \dots, 16}$$

4. C_{\min} – minimum blood concentration of C-reactive protein, IL-6 and soluble IL-6 receptor over the observation period.
5. t_{\min} – time to minimum blood concentration (C_{\min}) of C-reactive protein, IL-6 and soluble IL-6 receptor.

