11.2. Investigator's adherence to protocol

No deviations from the Protocol are allowed during the study without prior written permission from JSC BIOCAD, except when necessary to prevent any immediate danger to the volunteer.

Protocol deviation is any change, discrepancy, or deviation from the study design or procedures of the study Protocol.

Any protocol deviation in the course of the clinical study must be registered and reflected in the study documents.

All protocol deviations are classified as major or minor deviations.

A minor deviation from the Protocol is an unforeseen and unintended event that occurred during the study and contradicts the requirements of the Protocol, which does not significantly affect the rights, safety and well-being of the volunteer or the consistency, accuracy and reliability of the study data.

A major deviation from the Protocol (or a protocol violation) is a deviation that may affect the rights, safety of a volunteer or the consistency, accuracy, and reliability of the study data.

Examples of probable major protocol deviations:

- A volunteer met study exclusion criteria but was not excluded;
- A volunteer received a prohibited concomitant medication;
- A volunteer was included in the study without meeting the eligibility criteria;
- Study procedures were conducted without obtaining a written informed consent from a volunteer;

Translated from Russian to English, dated 06-Jul-2020

- Volunteer’s indiscipline, non-compliance with restrictions during participation in the study (taking alcohol, drugs);
- Errors in selection of doses/route of administration/drug storage;
- Protocol violations that may be considered by the clinical trial monitor or study coordinator to have an impact on the safety of participants or the consistency and reliability of the study data;
- Missing two or more of the scheduled blood samples for analysis of pharmacokinetics/pharmacodynamics;
- Any violation of the confidentiality of information about study participants.

Information about major deviations should be presented to the Sponsor and the local ethics committee. In case of any major protocol deviations, the volunteer must be excluded from the final PK/PD data analysis.

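### AUC0-1680 and AUMC0-1680 are computed at scheduled hours although sampling windows are allowed; use actual elapsed times, with a rule for reaching 1680 h

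*Combined protocol and SAP*

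**What the plan says.** Section 9.1.1 opens by saying that "the following pharmacokinetic variables will be estimated at time points specified in this protocol". For AUC0-1680 and again for AUMC0-1680 it takes C_p as the concentration at t_p and restricts t_p to "0; 2; 8; 12; 24; 48; 72; 96; 120; 168; 240; 336; 504; 672; 1176; 1680" hours, 16 values. CL, MRT, k_el, T1/2 and AUC0-inf are then built from those two sums.

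Section 9.1.2 does the same for CRP, IL-6 and soluble IL-6 receptor: "the following pharmacodynamic parameters will be calculated at the Protocol-specified time intervals", and AUC0-1680 "is calculated using the trapezoidal method with the following formula" on the identical list of hours.

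Off-schedule draws are foreseen. Table 4 in section 4.2 has a column headed "Acceptable window for blood sampling" (its entries are redacted). Section 6.6 classes a volunteer as non-compliant if he "Deviated from the scheduled window for pharmacokinetic and pharmacodynamic sampling by a time exceeding the acceptable deviation described in Tables 3 and 4". Section 5.3.1 lists among those who can be replaced "Non-compliant volunteers (see Section 6.6)", and section 11.2 adds: "In case of any major protocol deviations, the volunteer must be excluded from the final PK/PD data analysis".

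Section 4.2 starts the PK sampling clock at the last injection. Section 7.1 gives different rules (logarithmic trapezoid, regression on the terminal phase) but does not say whether scheduled or actual times are used. The body of section 9.5, on missing, non-evaluable and uncertain data, is redacted.

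**The concern.** A window means that a perfectly valid sample may be taken at a time other than the scheduled one. The formulas have no place for that time: the measured concentration is attached to the scheduled hour. Because the concentration is changing, the profile that is integrated is slightly wrong.

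AUC0-1680 and AUC0-inf are the primary PK endpoints, and every other PK parameter in 9.1.1 except Cmax and Tmax is derived from the same two sums. Cohorts 02 to 07 have three mandatory volunteers and cohort 01 has one, so error in single profiles averages out only a little. The error is also avoidable: the compliance rule in 6.6 cannot be applied unless the actual sampling times are recorded.

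**Working it through.** **Is the list the schedule?** The study flowchart (Table 9, section 4.6.1) gives days from injection 0, 1, 2, 3, 4, 5, 7, 10, 14, 21, 28, 49 and 70. Multiplied by 24 these are 0, 24, 48, 72, 96, 120, 168, 240, 336, 504, 672, 1176 and 1680 h. Adding the 2, 8 and 12 h draws gives exactly the 16 values in 9.1.1. So t_p is the nominal schedule.

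**Size for one sample.** In the elimination phase, a draw that is d hours late reads low by the factor 2^(−d/half-life). For a 14-day half-life (336 h) and d = 24 h the factor is 2^(−24/336) = 0.952, or 4.8% low. For d = 4 h it is 2^(−4/336) = 0.992, or 0.8% low. In the linear sum the 672 h sample carries a weight of (1176 − 504)/2 = 336 h, so late samples count heavily.

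**Random deviations, assumed windows.** These inputs are not in the documents: one-compartment subcutaneous model; half-widths of 0.1 to 1 h on day 1, 2 h on Days 3 to 6, 12 to 24 h up to Day 29, 48 h at Day 50 and 72 h at Day 71; sampling times uniform within the window; no assay noise. Errors are relative to the same formula with every sample on schedule. 95% ranges:

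| True half-life | AUC0-1680, nominal times | T1/2 = ln2 × MRT, nominal times | AUC0-1680, actual times brought to 1680 h |
|---|---|---|---|
| 7 d | −2.6 to +2.8% | −2.2 to +2.3% | −0.5 to +0.8% |
| 14 d | −2.0 to +2.1% | −1.8 to +2.0% | −0.4 to +0.5% |
| 21 d | −1.6 to +1.7% | −1.5 to +1.6% | −0.3 to +0.3% |

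The mean AUC error is below 0.1%. Halving the windows roughly halves the ranges, to about ±1%.

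**Sensitivity to window width and direction.** Assumed absorption half-life 2 d and elimination half-life 5 to 21 d. Half-widths are narrow (5 min to 4 h), mid (15 min to 24 h) or wide (30 min to 72 h). Nominal times, 9.1.1 formulas:

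| Deviations | AUC0-1680 | T1/2 = ln2 × MRT |
|---|---|---|
| Random, mean error, all widths | 0.00 to +0.36% | 0.00 to +0.32% |
| Random, SD per profile, all widths | 0.1 to 3.2% | 0.1 to 2.5% |
| All late, narrow | −0.2 to −0.4% | −0.2 to −0.5% |
| All late, mid | −2.3 to −5.6% | −0.7 to −4.0% |
| All late, wide | −5.0 to −9.0% | −2.4 to −8.1% |

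All-early deviations have the opposite sign and similar size (AUC up to +11.1%, T1/2 up to +8.6%, both with wide windows). For a cohort of three, the largest random SD of 3.2% becomes 3.2/√3 = 1.8% for the cohort mean.

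**Late visits only.** Suppose Day 50 is 48 h late and Day 71 is 72 h late, with a true half-life of 21 d. By the 9.1.1 formula T1/2 moves from 16.8 to 16.5 d (−1.9%) and AUC0-1680 by −1.5%. A terminal fit to the last three points, in the spirit of 7.1, is more sensitive: nominal 672, 1176 and 1680 h are equally spaced, so the slope is inflated by (1752 − 672)/(1680 − 672) = 1080/1008 = 1.071, and 21 d reads as 21/1.071 = 19.6 d.

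**Are actual times enough?** Not alone. With wide windows, random deviations and a 21 d half-life, moving to actual times lowers the AUC SD only from 1.49% to 0.83%, and the T1/2 SD goes from 1.11% to 1.27%. The reason is that the last sample no longer falls at 1680 h, so the sums cover a varying interval.

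**The case against.** The other side has good points, and several of them limit the claim.

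- A reader might infer that the planned AUC and half-life are biased. Under random deviations they are not, to any useful degree. Only deviations that run mostly one way produce a shift, and nothing in the documents says that they will.
- A reader might take the half-life error to be −7% to +8%. Under the same assumed windows that range belongs to a terminal-phase fit as in 7.1. The formula that fixes t_p, in 9.1.1, uses ln2 × MRT, which moves by about ±1.5 to 2.3%.
- A reader might infer that section 9.7 keeps volunteers whose samples fall outside the window, since its criteria do not mention timing. That is reading silence as a rule. Sections 6.6 and 5.3.1 make such volunteers non-compliant and replaceable, and 11.2 excludes major deviations from the PK/PD analysis. Larger deviations are therefore limited, although none of these rules touches a sample taken inside its window.
- The window widths are redacted, and a timing rule could sit in the redacted part of 9.5. Its title makes that unlikely for a valid in-window sample but does not rule it out.
- No decision depends on AUC. Escalation follows dose-limiting toxicity, and the stated hypothesis in section 3 concerns the maximum tolerated dose. Noise of 1 to 3% may also be small beside assay and between-subject variability, which the documents do not quantify.

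What remains is that the plan states a calculation rule, the rule is the wrong one wherever windows are used, and a better one costs almost nothing.

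**Conclusion.** The point holds as a modest, avoidable error in the primary PK endpoints and the parameters derived from them. The readable text fixes t_p at scheduled hours, expects off-schedule samples, and nowhere calls for actual times.

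Under windows of up to 72 h at Day 71 and a true half-life of 7 to 21 d, the 95% error range is about ±1.7 to 2.8% for AUC0-1680 and ±1.5 to 2.3% for T1/2. Windows of a few hours or less keep it well under 1%, even with every sample at the same edge. Errors above about 5% in AUC need windows of about a day or more together with deviations in one direction. The true size cannot be established while the widths are redacted.

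A separate matter should not be confused with this one. With perfectly timed samples, ln2 × MRT over 0 to 1680 h already differs from the true half-life by +42%, +14%, −1% and −20% at 5, 10, 14 and 21 d under the same model. Actual times do not cure that.

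**What to change.** 1. In 9.1.1 and 9.1.2, define t_p as the actual elapsed time from the last injection, the clock already set in section 4.2. Apply it to AUC, AUMC, Tmax, Tmin and any terminal fit.
2. State how both AUC and AUMC are brought to exactly 1680 h when the last sample is early or late: interpolation if it is late, a short extrapolation if it is early. Name one definition of k_el for this, because 9.1.1 (1/MRT) and 7.1 (terminal regression) now differ. For the PD markers, interpolate linearly or carry the last value. Without this rule, actual times give little gain at long half-lives.
3. Keep nominal times for by-visit concentration summaries and mean plots.
4. If the redacted part of 9.5 already covers timing, cross-refer to it and align the formulas.

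The cost is a change of wording and minor programming. The sampling times are already needed to judge compliance under 6.6, and sample size, significance level and visits are unchanged.

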1.2. Name and description (characteristics) of the test drug

1.2.1. Test drug

Trade name: not applicable. Product code: BCD-089.

National nonproprietary name: Anti-interleukin-6 receptor monoclonal antibody

Pharmaceutical form: solution for injection.

Composition per 1 mL:

Active substance: [REDACTED]

Excipients:

[REDACTED]

Manufacturer: JSC BIOCAD, Russia

Shelf life: 2 years.

Storage and transportation conditions:

[REDACTED]

Packaging:

[REDACTED]

Labeling:

In accordance with Article 46 of Federal Law “On the Circulation of Medicinal Products” No. 61-Φ3 of April 12, 2010, the primary packaging of the test drug contains the following Russian text in easily readable font:

Translated from Russian to English, dated 06-Jul-2020

[REDACTED]

[REDACTED]

Manufacturer: JSC BIOCAD, Russia

Shelf life: 2 years.

Storage and transportation conditions:

[REDACTED]

[REDACTED]

Packaging:

[REDACTED]

[REDACTED]

[REDACTED]

Labeling:

In accordance with Article 46 of Federal Law “On the Circulation of Medicinal Products” No. 61-Φ3 of April 12, 2010, the primary packaging of the test drug contains the following Russian text in easily readable font:

- “Diluent”,
- batch number,
- release date,
- expiry date,
- volume.

The secondary packaging contains the following information in Russian in easily readable font:

- name: “Diluent”,
- manufacturer name: JSC BIOCAD, Russia,
- batch number,
- release date,
- expiry date,
- method of administration,
- volume,
- storage conditions,

Translated from Russian to English, dated 06-Jul-2020

- cautionary information.

Primary and secondary packaging of the test drug will be additionally labeled with: “For clinical studies only”.

Method of administration and dosing regimen:

In this study, the drug will be administered as a single-dose subcutaneously. The administered dose of BCD-089 depends on the cohort into which the volunteer was assigned:

1. Cohort 01 - 1 volunteer to whom a single subcutaneous injection of BCD-089 at a dose of 0.06 mg/kg will be administered.
2. Cohort 02 - a maximum of 6 volunteers to whom a single subcutaneous injection of BCD-089 at a dose of 0.3 mg/kg will be administered.
3. Cohort 03 - a maximum of 6 volunteers to whom a single subcutaneous injection of BCD-089 at a dose of 0.625 mg/kg will be administered.
4. Cohort 04 - a maximum of 6 volunteers to whom a single subcutaneous injection of BCD-089 at a dose of 1.0 mg/kg will be administered.

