1.3.2. Clinical studies of the test drug

Not performed.

1.4. Summary of known and potential risks and benefits for clinical trial subjects (risk/benefit ratio)

Benefit evaluation

BCD-089 is an innovative drug, which has never been used in humans. The first stage of BCD-089 clinical development will be to evaluate its effects in healthy volunteers, which means that participants in such a study will not derive subjective (personal) benefits from their participation in it, except for a detailed medical examination; however, data obtained after the completion of this study will have high scientific value and may help introduce into clinical practice a new highly effective product for the treatment of severe autoimmune disorders.

Risk evaluation

[REDACTED]

Translated from Russian to English, dated 06-Jul-2020

[Redacted content]

Translated from Russian to English, dated 06-Jul-2020

[Redacted content]

Translated from Russian to English, dated 06-Jul-2020

1.5. Description and justification of the study design, the method of administration of the test drug, dose, dosing regimen and the course of treatment

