7. PHARMACOKINETICS AND PHARMACODYNAMICS ASSESSMENT

7.1 List of pharmacokinetic variables

To evaluate PK parameters of the drugs based on the data obtained on the concentration of anti-IL-6 receptor monoclonal antibody in the blood of volunteers, the following pharmacokinetic parameters will be calculated: the area under the "concentration-time" curve (AUC from the moment of administration of the drug to 1680 h (71 days after administration) and $AUC_{0-\infty}$ (to infinity), the maximum concentration of anti-IL-6 receptor monoclonal antibody in human serum, C_{max} , time to reach the maximum concentration, T_{max} , half-life, $T_{1/2}$, the elimination constant K_{el} and total clearance, CL, after a single-dose subcutaneous injection of the test drug. The values of the C_{max} and T_{max} will be calculated as the highest of the measured concentration values and the corresponding time of the observed maximum. The $AUC_{(0-t)}$ will be calculated using the logarithmic trapezoid method. The value of $AUC_{(0-\infty)}$ will be determined by the formula: $AUC_{(0-\infty)} = AUC_t + C_t/k_{el}$, where AUC_t is the area under the "concentration-time" curve from the moment of drug administration to the last measured BCD-089 concentration (in this study it is $AUC_{(0-1680h)}$), C_t and K_{el} are the calculated values of the drug concentration in the last sample (in this study – C_{1680h}) and the elimination constants, respectively. To calculate C_t and K_{el} , the final (monoexponential) section of the pharmacokinetic curve is described using nonlinear regression analysis.

Thus, the main PK parameters evaluated will include:

Primary:

- ✓ AUC_{0-1680} - area under the concentration-time curve from the administration of the drug to 1680 h (71 days after administration) and $AUC_{0-\infty}$ (to infinity).

Secondary:

- ✓ C_{max} (maximum serum concentration of anti-IL-6 receptor antibody);
- ✓ T_{max} (time to maximum concentration);
- ✓ $T_{1/2}$ (half-life),
- ✓ K_{el} (elimination rate constant),
- ✓ CL (total clearance).

Translated from Russian to English, dated 06-Jul-2020

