9. **The area under the concentration-time curve** for anti-IL-6 receptor monoclonal antibody **over the time interval from 0 to ∞ ($AUC_{0-\infty}$)**.

$$AUC_{0-\infty} = AUC_{0-1680} + \frac{C_{1680}}{k_{el}}, \text{ where}$$

Translated from Russian to English, dated 06-Jul-2020

C_{1680} – concentration of anti-IL-6 receptor antibody over the period equal to 1680 hours after the drug administration.

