9.2 Statistical analysis methods

The study results will be analyzed using the two-sided statistical hypotheses with a significance level of 0.05.

Translated from Russian to English, dated 06-Jul-2020

Quantitative and scale data

To describe quantitative and scale variables, it is planned to use the following characteristics: mean, median, standard deviation, quartiles, minimum and maximum, and coefficient of variance.

The statistical analysis of the obtained data will be conducted using SAS 10.0 software and the R programming language for statistical data processing. Mann-Whitney, Wilcoxon, Kruskal-Wallis, and Friedman tests will be used to compare quantitative and scaled data. The categorical data will be processed using the Fisher's exact test and the χ^2 Pearson test.

Quantitative data include the following parameters:

- Membrane receptor occupancy with BCD-089

Pharmacokinetics:

- Anti-human interleukin-6 receptor monoclonal antibody concentration
- Area under the curve
- Time (including time to maximum concentration, half-life period)
- Elimination characteristics (clearance, elimination constant)

Pharmacodynamics:

- Human IIL-6, C-Reactive Protein, soluble IL-6 receptor concentrations
- Area under the curve
- Time (including time to maximum concentration, trough concentration, time to achieve trough concentration)
- Elimination characteristics (clearance, elimination constant)

Tenderness:

Value specified in Visual Analogue Scale (out of 10 points)

Safety:

- Complete blood count parameters
- Blood biochemistry parameters
- ECG parameters
- Urinalysis parameters

Translated from Russian to English, dated 06-Jul-2020

- Blood pressure, wrist pulse rate and body temperature
- Size of an abnormal lesion at the injection site reactions
- Time of presence of the abnormal lesion at the injection site

Categorical data include the following parameters:

Pharmacodynamics:

- Proportion of samples showing the maximum signal for membrane IL-6 receptor occupancy

Safety:

- Nature of an abnormal lesion at the injection site
- Frequency of AEs and SAEs by severity grades
- Frequency of grade 3/4 toxicity events
- Frequency of injection-site reactions (total and depending on the type of the lesion)
- Proportion of subjects who developed any grade neutropenia in each cohort.
- Frequency of cases of premature discontinuation from the study due to an AE/SAE

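### Total clearance is defined as Dose/AUC0-1680 after subcutaneous dosing only: the area after 1680 h is left out, and the result is apparent clearance (CL/F)

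*Combined protocol and SAP*

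**What the plan says.** Section 9.1.1, item 5, defines total clearance, which "is determined by the ratio of the anti-IL-6 receptor monoclonal antibody dose" to AUC0-1680. Item 9 of the same section defines AUC0-inf as AUC0-1680 plus C1680/k_el, but item 5 does not use it. Section 7.1 lists "total clearance, CL, after a single-dose subcutaneous injection of the test drug" and gives no other formula for it. The synopsis and section 7.1 name CL as a secondary pharmacokinetic endpoint and place AUC0-inf among the primary ones.

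On the route, section 1.2.1 states: "In this study, the drug will be administered as a single-dose subcutaneously". No cohort is dosed intravenously. Section 1.4 adds: "BCD-089 is an innovative drug, which has never been used in humans". No readable section contains an F term or calls the parameter apparent clearance.

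Two related definitions differ between sections:

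- **AUC rule.** Section 7.1 names the logarithmic trapezoid; section 9.1.1 says only trapezoid. The item 3 formula does not survive in the text available to us, but the neighbouring AUMC formula and the AUC formula in section 9.1.2 are linear.
- **k_el.** Section 7.1 fits the terminal mono-exponential phase by nonlinear regression; section 9.1.1, item 7, sets k_el = 1/MRT.

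Finally, section 9.2 (Statistical analysis methods) lists "Elimination characteristics (clearance, elimination constant") under Pharmacodynamics as well as under Pharmacokinetics.

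**The concern.** Clearance is dose reaching the circulation divided by the area to infinity. The planned ratio departs from this in two ways. It stops the area at 1680 h, and it puts the full administered dose in the numerator under a name that implies F = 1.

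The truncation error grows with half-life. In a dose-escalation trial it can therefore differ between cohorts and distort the comparison of clearance across doses. The label matters to anyone who later sets the value beside a clearance from intravenous dosing.

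The pharmacodynamic list raises a separate point that needs no model: CRP, IL-6 and sIL-6R are not administered, so a dose-over-area clearance has no meaning for them.

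**Working it through.** The plan states no numerical clearance, so there is no figure to reproduce.

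**Identity.** Dose/AUC0-1680 = (CL/F) x (AUC0-inf/AUC0-1680). With exact areas the second factor is at least 1. Since F is at most 1, CL/F is at least CL.

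**Inputs from the plan.** The sampling times in hours are "0; 2; 8; 12; 24; 48; 72; 96; 120; 168; 240; 336; 504; 672; 1176; 1680" (section 9.1.1). The last is 1680/24 = 70 days, and the last two intervals are 504 h each.

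**Assumed inputs.** A one-compartment model with first-order absorption, ka = 0.2 and 0.4 per day, half-lives of 5 to 35 days, F of 0.5 to 0.8, and no assay noise. The readable text gives neither half-life nor F.

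**Truncation.** With k = ln 2/half-life and T = 70 days, the fraction of AUC0-inf lying after T is

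(ka e^(-kT) - k e^(-ka T)) / (ka - k),

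and the truncation factor is 1/(1 - fraction). Two examples with ka = 0.2, where the second exponential is negligible:

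- 14 days: k = 0.0495, e^(-kT) = 2^(-5) = 0.03125. Fraction = 0.2 x 0.03125/0.1505 = 0.0415; factor = 1.04.
- 28 days: k = 0.02476, e^(-kT) = 2^(-2.5) = 0.1768. Fraction = 0.2 x 0.1768/0.1752 = 0.202; factor = 1.25.

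The same profile was then evaluated at the 16 protocol times. AUC0-1680 was taken by linear trapezoid, and by a linear-up/log-down trapezoid (a purely logarithmic rule is undefined from a zero pre-dose value). The table gives the planned ratio divided by CL/F, with the range over the two ka values.

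| Half-life (d) | Exact area | Linear trapezoid | Log-down trapezoid |
|---|---|---|---|
| 5 | 1.00 | 0.96-0.97 | 1.01 |
| 7 | 1.00 | 0.96-0.97 | 1.01 |
| 10 | 1.01 | 0.98 | 1.01-1.02 |
| 12 | 1.02-1.03 | 0.99-1.00 | 1.02-1.03 |
| 14 | 1.04 | 1.01-1.02 | 1.04-1.05 |
| 21 | 1.12-1.13 | 1.11-1.12 | 1.12-1.14 |
| 28 | 1.23-1.25 | 1.22-1.24 | 1.23-1.26 |

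**Comparison between cohorts.** At equal volume, a half-life of 7 days in one cohort and 28 days in another is a true 4-fold difference in CL/F. With exact areas and ka = 0.2 it would be reported as 4 x 1.002/1.253 = 3.2-fold; with linear trapezoids, as 3.1- to 3.2-fold. From 14 to 28 days, a true 2-fold difference is reported as 1.6- to 1.7-fold.

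**Bioavailability.** CL/F divided by CL is 1/F: 1/0.8 = 1.25 and 1/0.5 = 2.0. A constant F cancels in any comparison between cohorts.

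**What Dose/AUC0-inf would give.** The entries are again divided by CL/F. The terminal slope here is taken from the last two samples.

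| k_el and AUC rule | 5-14 d | 21 d | 28 d | 35 d |
|---|---|---|---|---|
| 1/MRT, linear trapezoid | 0.96-0.98 | 1.01 | 1.06 | 1.12-1.13 |
| Terminal slope, linear trapezoid | 0.96-0.98 | 0.99 | 0.99 | 1.00 |
| Terminal slope, log-down trapezoid | 1.00-1.01 | 1.00 | 1.00 | 1.00 |

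Changing the denominator alone therefore leaves about 6% error at 28 days and 12% at 35 days if k_el stays at 1/MRT. With the terminal slope and the logarithmic rule, both already named in section 7.1, the model error is within about 1%.

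**The case against.** The strongest reply is that the effect may be negligible. Section 1.5.1 asserts that the follow-up suffices for full pharmacokinetics, and at a half-life of 10 days or less truncation is about 1%. CL is one of five secondary pharmacokinetic endpoints. AUC0-inf is reported separately, so a reader could derive Dose/AUC0-inf from the planned outputs. Section 7.1 already ties CL to a subcutaneous injection, and for further subcutaneous dosing CL/F is the useful quantity. All of this stands. It limits the size of the point but does not make the formula or the name right.

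Several stronger readings are tempting and are not supported:

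- **That clearance is overstated on both counts, whatever the half-life.** With linear trapezoids, the overestimate of area across the sparse late samples cancels or exceeds the truncation below about 12 days, and the ratio to CL/F is then slightly under 1. The offset is accidental, but an unconditional direction cannot be claimed.
- **That a fall of clearance with dose would be hidden.** A true 4-fold fall still appears as about 3-fold. That is attenuation.
- **That the factor 1/F is a numerical error in the analysis.** Dose/AUC0-inf carries the same factor; only the label can cure it.
- **That the pharmacodynamic elimination constant is undefined too.** A rate constant needs no dose, and section 7.2 uses one to obtain AUC0-inf for the markers. Only clearance lacks meaning there.
- **That this CL will set phase II doses.** Objective 1 (section 2.2) refers to a safe dose range and escalation follows dose-limiting toxicity. No readable section assigns CL that role.

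**Conclusion.** The point holds as a correction of formula and label for a secondary endpoint. That the area is truncated, that F cannot be estimated here, and that clearance is undefined for the three markers all follow from the text without assumptions.

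The numerical size rests on the assumed model and half-life. It is within about 5% of CL/F in either direction at 5 to 14 days and becomes material from about 21 days. The 1/F range rests on an assumed F. Sections on animal pharmacokinetics are redacted and may narrow both ranges. The correction should be made, but it does not affect the conduct of the trial.

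**What to change.** 1. In section 9.1.1 item 5, section 7.1 and the endpoint lists (synopsis and section 4.1.1), write: apparent clearance, CL/F = Dose/AUC0-inf.
2. Compute AUC0-inf with the terminal-slope k_el described in section 7.1, in place of 1/MRT.
3. State one AUC rule in sections 7.1 and 9.1.1. The logarithmic trapezoid of section 7.1, with linear steps while concentrations rise, performs best in the check above.
4. Report the extrapolated percentage of AUC0-inf for each volunteer.
5. In section 9.2, delete clearance from the pharmacodynamic list. Keep or remove the pharmacodynamic elimination constant consistently with its use in section 7.2.

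The cost is a few text edits and slightly more analysis work, including a terminal-phase fit per volunteer. No new samples, visits or data are needed.
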